6.4. WINDOWING CONVENTIONS

Unless otherwise specified, visit data as recorded in the database will be used for the analysis. No visit windowing recalculation will be performed for this trial.

6.5. STATISTICAL TESTS

The default significance level will be (5%); confidence intervals will be 95% and all tests will be two-sided, unless otherwise specified in the description of the analyses.

6.6. COMMON CALCULATIONS

For quantitative measurements, change from baseline will be calculated as:

- Test Value at Visit X – Baseline Value

6.7. SOFTWARE VERSION

All analyses will be conducted using SAS version 9.4 or higher.

Document: \\ieedc-nas01a\Boehringer_Ingelheim\BI_695501\XXA39605\Biostatistics\Documentation\SAP\15
-v2.0\BI 1297.12 SAP v2.0 31JAN2018.docx

Author: Version Number: 2.0
Version Date: 31JAN2018

Template No: CS_TP_BS016 Revision 4
Effective Date: 01Apr2016

Reference: CS_WI_BS005

7. STATISTICAL CONSIDERATIONS

7.1. ADJUSTMENTS FOR COVARIATES AND FACTORS TO BE INCLUDED IN ANALYSES

The following covariates and factors are used in the primary and secondary efficacy analyses. For details of their inclusion in the models, see the specific analysis section.

- Treatment (BI 695501 or US-sourced Humira)
- Baseline PASI
- Prior exposure to a biologic agent (Yes / No).

7.2. MULTICENTER TRIAL

This trial will be conducted by multiple investigators at multiple centers internationally, approximately 50 clinical sites across approximately 10 countries. Randomization to treatment arms is stratified by prior exposure to biological agent. No stratification by site was planned because of the small number of subjects to be randomized per site.

7.3. MISSING DATA

Missing safety data will not be imputed, unless otherwise specified in section 16.

Missing efficacy data will be handled as described in section 15.

Calculation for a partial date is described in APPENDIX 2.

7.4. MULTIPLE COMPARISONS/ MULTIPLICITY

No multiplicity consideration is required in this trial.

7.5. EXAMINATION OF SUBGROUPS

Subgroup analyses will be performed if the smallest group includes at least 10% of the randomized subjects.

Document: \\eedc-nas01a:\Boehringer_Ingelheim\BI_695501\XXA39605\Biostatistics\Documentation\SAP\15
-v2.0\BI 1297.12 SAP v2.0 31JAN2018.docx

Author: Version Number: 2.0
Version Date: 31JAN2018

Template No: CS_TP_BS016 Revision 4
Effective Date: 01Apr2016

Reference: CS_WI_BS005

7.5.1. REGION

A further subgroup analysis will be performed to evaluate the impact of the region on the primary efficacy endpoint. For this purpose, region will be defined as:

USA

Non-USA (Other countries)

7.5.2. PRIOR USE OF BIOLOGICAL AGENT

A further subgroup analysis will be performed to evaluate the impact of the stratification factor on the primary efficacy endpoint. For this purpose, the following stratification factor will be considered: prior use of biological agent Yes/No.

8. OUTPUT PRESENTATIONS

APPENDIX 1 shows conventions for presentation of data in outputs.

The templates provided with this SAP describe the presentations for this trial and therefore the format and content of the summary tables, figures, and listings to be provided by Biostatistics.

9. DISPOSITION AND WITHDRAWALS

All subjects who provide informed consent will be accounted for in this trial.

The counts of the analysis sets will be presented:

- All Subject Enrolled Set (ENR)
- All Subjects Randomized Set (RND)
- Full Analysis set (FAS)
- Per Protocol Analysis Set (PPS)
- Safety Analysis Set (SAF)
-

The reasons for exclusion from the analysis sets will be listed.

The following subject disposition and withdrawals will be presented for the ENR set:

Document: \\ieedc-nas01a:\Boehringer_Ingelheim\BI_695501\XXA39605\Biostatistics\Documentation\SAP\15
-v2.0\BI 1297.12 SAP v2.0 31JAN2018.docx

Author: Version Number: 2.0
Version Date: 31JAN2018

Template No: CS_TP_BS016 Revision 4
Effective Date: 01Apr2016

Reference: CS_WI_BS005

Statistical Analysis Plan

- Screened
- Rescreened
- Screen failure (defined as withdrawn from trial prior to randomization). The information will be displayed only once for subjects being rescreened and will correspond to the last information available in the eCRF.
- Primary reason for non-inclusion. The information will be displayed only once for subjects being rescreened and will correspond to the last information available in the eCRF.
- Randomized
- Randomized but not treated
- Treated
- Subjects with PASI 50 at Day 113 (Week 16)
- Subjects treated after Day 113 (Week 16)
- Completed treatment at Day 169 (Week 24)
- Completed the trial
- Discontinued from treatment strictly before Day 113 (Week 16), primary reason for premature discontinuation from treatment before Day 113 (Week 16)
- Discontinued from treatment, primary reason for premature discontinuation from treatment
- Discontinued from trial, primary reason for premature discontinuation from trial

The following subject disposition and withdrawals will be presented for the ENR set per site:

- Screened
- Rescreened
- Screen failure (defined as withdrawn from trial prior to randomization). The information will be displayed only once for subjects being rescreened and will correspond to the last information available in the eCRF.
- Randomized

Document: \\ieedc-nas01a:\Boehringer_Ingelheim\BI_695501\XXA39605\Biostatistics\Documentation\SAP\15-v2.0\BI 1297.12 SAP v2.0 31JAN2018.docx

Author: Version Number: 2.0
Version Date: 31JAN2018

Template No: CS_TP_BS016 Revision 4
Effective Date: 01Apr2016

Reference: CS_WI_BS005

- Randomized but not treated
- Treated
- Subjects with PASI 50 at Day 113 (Week 16)
- Subjects treated after Day 113 (Week 16)
- Completed treatment at Day 169 (Week 24)
- Completed the trial

9.1. IMPORTANT PROTOCOL DEVIATIONS

Protocol violations (as defined in section 5.4), as well as inclusion and exclusion criteria violators will be tabulated and listed for the FAS.

Separately, important protocol violations (not systematically excluding from PPS) are defined as:

- entering the study even though the subject did not satisfy the entry criteria;
- developing withdrawal criteria during the study but the subject did not withdraw;
- receiving the wrong treatment or incorrect dose;
- receiving a prohibited concomitant treatment.

Important protocol violations confirmed by a clinical and medical review as recorded in the protocol deviations log will be tabulated and listed for the FAS. These violations are not necessarily excluding subjects from the PPS (for exclusions from PPS refer to section 5.4).

The full protocol deviations log will be attached to the clinical study report.

10. DEMOGRAPHIC AND OTHER BASELINE CHARACTERISTICS

No statistical testing will be carried out for demographic or other baseline characteristics.

The following demographic characteristics will be reported at Primary Analysis for the FAS, PPS, SAF, and at Final Analysis for RND, FAS, PPS, and SAF:

- Age (years) at Informed Consent
- Category of age groups at Informed Consent

Document: \\ieedc-nas01a:\Boehringer_Ingelheim\BI_695501\XXA39605\Biostatistics\Documentation\SAP\15-v2.0\BI 1297.12 SAP v2.0 31JAN2018.docx

Author: Version Number: 2.0
Version Date: 31JAN2018

Template No: CS_TP_BS016 Revision 4
Effective Date: 01Apr2016

Reference: CS_WI_BS005

Statistical Analysis Plan

- Adolescent (12-17 years): 12 <= AGE < 18 – no patient expected
- Adults (18-64 years): 18<= AGE < 65
- Adults (65-84 years): 65<= AGE < 85
- Adults (Over 85 years): 85<= AGE – no patient expected
- First age category at Informed Consent
 - AGE < 65 years
 - AGE >= 65 years
- Second age category at Informed Consent
 - AGE < 65 years
 - 65 <= AGE < 76
 - 76 <= AGE <85
 - AGE >= 85
- Gender (Male/Female)
- Childbearing potential (Post-Menopausal / Surgically Sterile / Childbearing Potential (includes tubal ligation))
- Race (American Indian or Alaska Native / Asian / Black or African American / Native Hawaiian or Other Pacific Islander / White / Other)
- Ethnicity (Hispanic or Latino / Not Hispanic or Latino / Not reported/ Unknown)
- Country
- Weight at baseline (kg)
- Height at baseline (cm)
- BMI at baseline (kg/m²)

The randomization stratification categories (Prior exposure to a biological agent Yes/No) based on eCRF data, will be presented at Primary and Final Analyses for the FAS.

The following baseline disease characteristics will be presented at Primary Analysis for the FAS, SAF, and at Final Analysis for FAS, PPS, and SAF:

- PASI score at baseline as collected in the eCRF
- Static Physician's Global Assessment of psoriasis (sPGA) score at baseline

Document: \\ieedc-nas01a:\Boehringer_Ingelheim\BI_695501\XXA39605\Biostatistics\Documentation\SAP\15-v2.0\BI 1297.12 SAP v2.0 31JAN2018.docx

Author:

Version Number:

2.0

Version Date:

31JAN2018

Template No: CS_TP_BS016 Revision 4

Reference: CS_WI_BS005

Effective Date: 01Apr2016

- Dermatology Life Quality Index (DLQI) score at baseline
-

Other baseline characteristics will be presented on FAS, and SAF:

- Infection screen (for HBsAg, HCV and HIV test)
- Chest X-Ray result
- Tuberculosis (TB) test
-

Accountability for missing data will be displayed in case of any missing entries.

10.1. DERIVATIONS

- Conversion factors:
 - 1 lbs=0.453592 kg
 - 1 in=2.54 cm
- BMI (kg/ m²) = weight (kg)/ height (m²)
- DLQI

The questionnaire will be analysed under 6 headings as follows:

Domain	Question Number	Score
Symptoms and feelings	Questions 1 and 2	Score maximum 6
Daily activities	Questions 3 and 4	Score maximum 6
Leisure	Questions 5 and 6	Score maximum 6
Work and school	Question 7	Score maximum 3
Personal relationships	Questions 8 and 9	Score maximum 6

Document: \\eedc-nas01a:\Boehringer_Ingelheim\BI_695501\XXA39605\Biostatistics\Documentation\SAP\15-v2.0\BI 1297.12 SAP v2.0 31JAN2018.docx

Author: Version Number: 2.0
Version Date: 31JAN2018

Template No: CS_TP_BS016 Revision 4
Effective Date: 01Apr2016

Reference: CS_WI_BS005

Treatment	Question 10	Score maximum 3
-----------	-------------	-----------------

Every item score ranges from 0 (Not relevant/Not at all) to 3 (Very much). The domain score is obtained by summing the score of the corresponding items.

DLQI total score is calculated by summing the scores of each question resulting in a range of 0 to 30 where 0-1 = no effect on subject's life, 2-5 = small effect, 6-10 = moderate effect, 11-20 = very large effect, and 21-30 = extremely large effect on subject's life. The higher the score, the more the quality of life is impaired. If the answer to 1 question in a domain is missing, that domain is treated as missing and the score calculated by summing the score of the 5 non-missing domains. If 2 or more questions are left unanswered (missing), DLQI total score is treated as missing.

-

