5.2.3 Dermatology Life Quality Index

The DLQI is a subject-administered, ten-question, quality of life questionnaire that covers 6 domains including symptoms and feelings, daily activities, leisure, work and school, personal relationships and treatment ([R05-2548](#)). The DLQI has a one-week recall period. Item scores range from 0 (not relevant) and 1 (not at all) to 3 (very much). Question 7 is a “yes”/ “no” question where “yes” is scored as 3.

The DLQI will be self-administered by the patient at visits indicated in the [Flow Chart](#).

The DLQI will be analyzed under 6 headings as follows ([R05-2548](#)):

Domain	Question Number	Score
Symptoms and feelings	Questions 1 and 2	Score maximum 6
Daily activities	Questions 3 and 4	Score maximum 6
Leisure	Questions 5 and 6	Score maximum 6
Work and school	Question 7	Score maximum 3
Personal relationships	Questions 8 and 9	Score maximum 6
Treatment	Question 10	Score maximum 3

DLQI total score is calculated by summing the scores of each question resulting in a range of 0 to 30 where 0-1 = no effect on subject’s life, 2-5 = small effect, 6-10 = moderate effect, 11-20 = very large effect, and 21-30 = extremely large effect on subject’s life. The higher the score, the more the quality of life is impaired. If the answer to 1 question in a domain is missing, that domain is treated as missing. If 2 or more questions are left unanswered (missing), DLQI total score is treated as missing. A 5-point change from Baseline is considered a clinically important difference ([Figure 10.2: 3](#)).

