15.2.1.4. DLQI

The proportion of patients achieving a DLQI of 0 or 1 at Week 16 will be assessed.

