15.2.2. MISSING DATA METHODS FOR SECONDARY EFFICACY VARIABLE(S)

Missing PASI 75 at Week 24 as well as missing sPGA and DLQI at Week 16 will be imputed using the combination of NRI and LOCF methods as missing data method considering NRI at Week 24 or Week 16 according to the variable considered (see Section 15.1.2.4).

Document: \\ieedc-nas01a:\Boehringer_Ingelheim\BI_695501\XXA39605\Biostatistics\Documentation\SAP\15-v2.0\BI 1297.12 SAP v2.0 31JAN2018.docx

Author: Version Number: 2.0
Version Date: 31JAN2018

Template No: CS_TP_BS016 Revision 4
Effective Date: 01Apr2016

Reference: CS_WI_BS005

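### The SAP's DLQI rule for one blank item also discards an answered item, so some patients whose recorded answers total 2 to 4 count as Week 16 DLQI 0/1 responders

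*SAP*

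**What the plan says.** The Week 16 endpoint is given in SAP 15.2.1.4 in one sentence: "The proportion of patients achieving a DLQI of 0 or 1 at Week 16 will be assessed". That section contains no derivation and no cross-reference. The only DLQI scoring rule in the SAP is in section 10.1, under baseline characteristics. It has four relevant parts:

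- Item coding: "Every item score ranges from 0 (Not relevant/Not at all) to 3 (Very much").
- Total: the sum over all questions, "resulting in a range of 0 to 30 where 0-1 = no effect on subject's life, 2-5 = small effect, 6-10 = moderate effect".
- One unanswered question: "that domain is treated as missing and the score calculated by summing the score of the 5 non-missing domains".
- More than one unanswered: "If 2 or more questions are left unanswered (missing), DLQI total score is treated as missing".

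Protocol 5.2.3 has the first half of the one-blank rule, "If the answer to 1 question in a domain is missing, that domain is treated as missing", but does not say how the total is then formed. The five-domain sum is an SAP addition.

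SAP 15.2.2 covers absent values: "Missing PASI 75 at Week 24 as well as missing sPGA and DLQI at Week 16 will be imputed", using non-responder imputation combined with LOCF.

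**The concern.** Four domains contain two questions each: symptoms and feelings ("Questions 1 and 2"), daily activities, leisure, and personal relationships. If one question of a pair is blank, the rule removes both from the total. The answered one is in effect scored 0 whatever the patient ticked. Nothing is rescaled, so a total built from five domains is held against the same 0/1 cut-off as a total built from six.

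This conflicts with the same paragraph, which defines the total as a sum over every question. The missing-data rule in SAP 15.2.2 does not rescue it either: a five-domain total is not missing, so it enters the analysis as observed. At stake is whether a named secondary responder rate includes patients whose own recorded answers already put them above the cut-off.

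**Working it through.** Inputs: item range 0 to 3, domain composition, bands and missing-item rules from SAP 10.1; responder cut-off from SAP 15.2.1.4; about 300 patients randomized 1:1 (Protocol 3.1), so 150 per arm.

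**1. Reproduce the stated range.** Domain maxima: 6 + 6 + 6 + 3 + 6 + 3 = 30, as the SAP states. With a two-item domain dropped the maximum is 30 − 6 = 24; with a single-item domain dropped (question 7 or 10) it is 30 − 3 = 27. The cut-off does not move in either case.

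**2. Notation for one blank in a two-item domain.** Let S be the sum of the other five domains (the SAP total), c the answered companion item (0 to 3) and b the unknown blank item (0 to 3).

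- Sum of the answered items: A = S + c
- True total: T = S + c + b

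Since S ≤ A ≤ T, anyone with A of 0 or 1 also has S of 0 or 1, but not the reverse. Compared with summing the answered items, the SAP rule can therefore only add responders.

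**3. Examples.**

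| Answers | SAP total S | Answered sum A | Possible true total T |
|---|---|---|---|
| Question 1 = 3, question 2 blank, rest 0 | 0 (responder) | 3 (small effect) | 3 to 6 |
| Question 1 = 3, question 2 blank, question 10 = 1, rest 0 | 1 (responder) | 4 (small effect) | 4 to 7 |

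**4. Bounds.** For a patient scored 0 or 1 (S ≤ 1): A ≤ 1 + 3 = 4, and T ≤ 4 + 3 = 7. For a blank question 7 or 10 there is no companion item, so A = S ≤ 1 and T ≤ 4; no recorded answer is lost.

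**5. How many answer patterns are affected.** With one blank in a two-item domain, the other five domains hold 8 items. S = 0 arises in 1 way and S = 1 in 8 ways. With 4 possible companion values, (1 + 8) × 4 = 36 patterns score 0 or 1. Those with A ≥ 2 are:

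- S = 0 with c = 2 or 3: 1 × 2 = 2
- S = 1 with c = 1, 2 or 3: 8 × 3 = 24

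That is 26 of 36. In these the true total cannot be 0 or 1, whatever the blank would have been. This counts patterns and is not a probability, since patterns are not equally likely. For a blank question 7 or 10 the corresponding count is 0 of 10.

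**6. Size.** The documents give no rate of single blanks. Assume a fraction f of patients has exactly one, and a fraction g of those is reclassified. Shift in response rate = f × g.

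| f | g | Shift (percentage points) | Patients per arm of 150 |
|---|---|---|---|
| 1% | 10% | 0.1 | 0.15 |
| 1% | 50% | 0.5 | 0.75 |
| 5% | 10% | 0.5 | 0.75 |
| 5% | 50% | 2.5 | 3.75 |

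**The case against.** The strongest reply is that nothing in the trial turns on this. The protocol synopsis makes the secondary efficacy results descriptive, equivalence is decided on PASI 75 alone, and the DLQI result is reported as a risk difference with the same rule applied blind to both arms. Blanks should also be few: the questionnaire is completed at the site (Protocol 6.1) and the form itself asks patients to check that every question is answered. All of this stands, and it limits the importance of the point. It does not make the rule correct.

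Three stronger readings are tempting and should not be drawn:

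- A reader might infer that badly affected patients are counted as responders. The bounds exclude that. One item can be at its maximum, but the answered items total at most 4 (small effect) and the true total at most 7 (moderate effect).
- A reader might take the assumed blank rate itself, 1 to 5 percentage points, as the overstatement. That needs every questionnaire with a blank to change class. A change requires the blank to fall in a two-item domain, the other five domains to total 0 or 1, and the companion answer to lift the sum to 2 or more.
- A reader might infer that the rule biases the comparison or the equivalence conclusion. The documents give no sign of different blank rates by arm, and PASI 75 does not use the DLQI.

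Two further objections stand in part. Applying section 10.1 at Week 16 is an inference, though no other DLQI rule exists in the SAP. And scoring the blank as 0, as proposed below, also errs downward: with question 1 = 1, question 2 blank but truly 3, and the rest 0, the patient scores 1 and remains a responder when the true total is 4. That error is smaller, because it comes only from the unknown answer and not from a known one, but it must be stated.

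**Conclusion.** The rule is wrong as written. It discards recorded answers, contradicts the SAP's own definition of the total, and can label as responders patients whose answers rule that out. Relative to summing the answered items, the error runs only toward response.

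The likely effect is small: 0.1 to 2.5 percentage points on the response rate, resting entirely on the assumed 1% to 5% of patients with one blank and 10% to 50% of those reclassified. It touches one descriptive secondary endpoint, and only when the blank is one of the 8 questions in two-item domains. It is worth correcting because the correction is nearly free, not because the trial's conclusion is at risk.

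**What to change.** Amend the sentence in SAP 10.1. With exactly one unanswered question, compute the DLQI total from all nine answered questions, with the blank scored 0. Leave only that domain's score missing. Keep the existing rule that two or more blanks make the total missing. Add to SAP 15.2.1.4 a statement that this derivation applies at Week 16.

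State that some downward bias remains from the unknown item. As a check, rerun the endpoint treating as missing, under the non-responder/LOCF rule of SAP 15.2.2, any total whose 0/1 status depends on the blank. These are the questionnaires with one blank and an answered sum of 0 or 1; at 2 or more the patient is a non-responder whatever the blank would have been.

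Cost: one SAP sentence, one derivation line, a cross-reference and one supplementary run. The reported response rate may fall slightly, and baseline DLQI totals with one blank may rise, since they use the same derivation.

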11. SURGICAL AND MEDICAL HISTORY

Surgical and Medical History information will be presented at Primary Analysis for the SAF, at Final Analysis for the FAS, PPS and SAF.

Surgical and Medical History will be coded using MedDRA version 19.1 or higher.

The system organ classes will be sorted by internationally agreed EMA SOC order (refer to APPENDIX 3), preferred terms will be sorted by decreasing frequencies (within system organ class).

Data captured on the "Medical History and Previous surgical procedures" page of the eCRF will be assigned to prior or concomitant.

See APPENDIX 2 for handling of partial dates for medical history, surgeries and procedures; if it is not possible to define a history, surgery or procedure as prior, concomitant, or post-treatment, it will be classified by the worst case; i.e., concomitant.

- Prior medical history, surgeries, and procedures are defined as those conditions or procedures which stop prior to or at Screening.
- Concomitant medical history, surgeries, and procedures are defined as those conditions or procedure which:
 - started prior to or at Screening and are ongoing or active at the date of Screening
 - or
 - started after Screening during the treatment period.

Document: \\ieedc-nas01a:\Boehringer_Ingelheim\BI_695501\XXA39605\Biostatistics\Documentation\SAP\15-v2.0\BI 1297.12 SAP v2.0 31JAN2018.docx

Author: Version Number: 2.0
Version Date: 31JAN2018

Template No: CS_TP_BS016 Revision 4
Effective Date: 01Apr2016

Reference: CS_WI_BS005

For rescreened patient the latest Screening information will be considered.

Prior and concomitant surgical and medical history will be presented by SOC (System Organ Class) and PT (Preferred Term) in two separate tables.

12. MEDICATIONS

Medications will be presented at Primary and Final Analyses for the FAS, PPS, and SAF. They will be coded using the WHO Drug Dictionary version SEP2016 or higher.

No ATC class coding will be performed. The medical terms will be summarized by WHO-DD Preferred Name. The WHO-DD Preferred Name will be sorted by decreasing frequencies.

See APPENDIX 2 for handling of partial dates for medications, in the case where it is not possible to define a medication as prior, concomitant, or post treatment, the medication will be classified by the worst case; i.e., concomitant.

- ‘Prior’ medications are medications which started and stopped prior to the first dose of trial medication.
- ‘Concomitant’ medications are medications which:
 - started prior to, on, or after the first dose of trial medication and started no later than end of trial medication,
 - AND ended on or after the date of first dose of trial medication or were ongoing at the end of the trial.
 - ‘Post’ medications are medications which started after the last dose of trial medication.

In addition, concomitant medications will be allocated to Period 1 as follows:

- Period 1: Concomitant medication with start date prior to Week 16 visit date, and [end date after randomization or ongoing at the end of the trial].

